9.2 Safety

Data concerning safety and the registration of adverse events will be collected.

10. PATIENT SAFETY

10.1 Safety instructions

The PET tracers are well tolerated and safe without reported clinically significant adverse events. Allergic reactions could occur in a very low percentage of patients as in routine clinical practice, due to the injection of gadolinium-based paramagnetic contrast medium during PET/MR examinations.

The assessment of the safety of the experimental examination will consist in monitoring and recording adverse events and serious adverse events.

10.2 Definitions of Adverse Event, Adverse Drug Reaction and Serious Adverse Event, Serious Adverse Reaction

Adverse events

Information about all adverse events, whether spontaneously reported by the subject, or those experienced by physician specific questions, such as those highlighted by the patient's physical examination, laboratory or other investigations, will be collected, registered on the Case Report Form (CRF) and followed as appropriate.

An event is defined as any sign, symptom or unplanned clinical condition occurring after the PET/MR examination, although there is no causal relationship between the event and the radiotracer administered.

Information about all serious adverse events will be collected and recorded on the Sample Adverse Event Reporting Module. To ensure patient safety, all serious adverse events must be reported within 24 hours of the researcher who is aware of it.

Severe Events are defined as those adverse events that:

- are fatal;
- put the patient in danger of life;
- require patient admission or prolong hospital stay;
- they involve significant and persistent disability / inability but not necessarily permanent;
- they are significant from the medical point of view in the sense that they can harm the patient and require medical or surgical intervention to prevent the above listed situations.

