6.2 Duration of study

Total duration of the study: 3 years.

For each patient the time of patient direct involvement will be approximately 2 hours for each PET/MR study (duration: approximately 1h after i.v. administration and approximately 1h for the duration of each PET/MR examination).

The patients will be followed-up up to until the end of the study period.

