8. TREATMENTS

In addition to the execution of 68Ga-PSMA PET/MR and 68Ga-Bombesin PET/MR scans, all the other imaging procedures and treatment strategies performed will be in the course of routine work-up patient management.

68Ga-PSMA PET/MR and 68Ga-Bombesin PET/MR study:

Tracers synthesis will be performed in our Department following IMPD. 68Ga-PSMA PET/MR study will start 60 minutes after the administration of 160 ± 50 MBq of 68Ga-PSMA and 68Ga-Bombesin study will start 45 minutes after the administration of 140 ± 50 MBq of 68Ga-Bombesin. For both scans the following protocol will be applied:

- localizer MR scans to define the number of table positions (PET-FOV) to acquire (4-min/table position); specific attenuation correction and anatomical localization MR sequences at each PETFOV; pelvic multi-parametric MR protocol according to European Society of Urogenital Radiology (ESUR) guidelines.
Gadolinium-based paramagnetic contrast agent will be injected intravenously with a dose of 0.1mmol/kg and an injection rate of 4 ml/sec. The MR protocol may be modified according to specific clinical requirements.

- PET-acquisition will start from the mid-thigh to the base of the skull base to exploit the reduced ⁶⁸Ga-PSMA and ⁶⁸Ga-Bombesin ligand uptake in the urinary system after pre-scan voiding. Acquisition should proceed from the lower end of the axial field of view cranially in order to minimize misalignment for the urinary bladder which tends to fill up during the time of the examination. PET scans will be acquired in three-dimensional (3D) mode with an acquisition time of usually 2–4 min per bed position. Overall, PET coverage will be identical to the anatomical MR scan range.

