10.3 Pharmacovigilance Procedure

Information about all serious adverse events will be collected and recorded on the Sample Adverse Event Reporting Module. To ensure Patient safety, all serious adverse events must be reported within 24 hours of the researcher who is aware of it.

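### The adverse event definition in section 10.2 starts only after the PET/MR examination, so read literally it leaves out tracer uptake and the scan itself

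*Combined protocol and SAP*

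**What the plan says.** Section 10.2 sets the time window for an adverse event: "An event is defined as any sign, symptom or unplanned clinical condition occurring after the PET/MR examination". The rest of that sentence removes any need for a causal link to the tracer and does not alter the timing. The serious category is then built on the first definition: "Severe Events are defined as those adverse events that" meet one of five listed criteria. Sections 10.2 and 10.3 both require that "all serious adverse events must be reported within 24 hours of the researcher who is aware of it".

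Section 10.1 describes the purpose: "The assessment of the safety of the experimental examination will consist in monitoring and recording adverse events and serious adverse events". It also names one foreseeable hazard, allergic reaction to the gadolinium contrast injected during the examination.

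Section 8 gives the order of events on a scan day: "68Ga-PSMA PET/MR study will start 60 minutes after the administration of" the first tracer's activity, and "68Ga-Bombesin study will start 45 minutes after the administration of" the second's. Within the scan protocol, "Gadolinium-based paramagnetic contrast agent will be injected intravenously". Section 6.2 splits each session into "approximately 1h after i.v. administration and approximately 1h for the duration of each PET/MR examination". Under Study procedures, the Synopsis puts the two sessions on different days, more than 48 hours apart and within one month.

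**The concern.** All the study exposures come before the point at which the definition starts to count. The tracer is injected 45 to 60 minutes before scanning, and the contrast is given during the scan. A transient reaction to either could begin and end before the examination is over. Staff who follow 10.2 as written would have no reason to enter it on the CRF. If it met a seriousness criterion, it would also fall outside the definition that triggers 24-hour reporting.

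The protocol conflicts with itself here. Section 10.1 makes the examination the object of safety monitoring and names a reaction to contrast given during it, while 10.2 literally excludes such a reaction if it resolves on the scanner.

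The wording is also singular although each patient has two examinations. One reader may hold that the whole second session already falls after the first examination and is covered. Another may hold that the clock restarts at the end of each examination. The text does not settle this.

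Both tracers are investigational products, and recording adverse events is the whole of the stated safety assessment. A clean safety record would be hard to interpret if the definition omits the hours of exposure.

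**Working it through.** The plan gives no figure on this point to reproduce. The check has three parts: whether any other text sets an earlier start, how much time is left out, and what that could mean in events.

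**1. Is there an earlier start elsewhere?**

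- Section 9.2 and the Synopsis safety criteria promise that adverse events will be collected, with no start time.
- The general collection sentence in 10.2 covers all adverse events, again with no start time, and depends on the definition that follows it.
- Section 10.3 repeats the 24-hour rule with no window of its own.
- The flow chart (section 2) has no adverse event row.
- The heading of 10.2 announces definitions of adverse drug reaction and serious adverse reaction. The text defines neither, so no separate term catches injection reactions.
- The Synopsis describes a study of about 2 hours that includes the waiting time, whereas 6.2 counts waiting and examination separately. On either description, the period after the examination begins when the scan ends.

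Nothing in the documents moves the start earlier.

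**2. Time outside the literal definition**

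Inputs: uptake of 60 min (68Ga-PSMA) and 45 min (68Ga-Bombesin) from section 8; about 60 min of uptake and about 60 min of examination from 6.2; 60 patients from 7.1.

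Time left out per session = uptake + examination.

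- 68Ga-PSMA: 60 + 60 = 120 min.
- 68Ga-Bombesin: 45 + 60 = 105 min with the section 8 uptake time, or 60 + 60 = 120 min with the 6.2 figure.

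| Reading of 10.2 | Per patient | 60 patients |
|---|---|---|
| First examination only | 105 to 120 min | 60 × 105/60 = 105 h to 60 × 120/60 = 120 h |
| Each examination | 120 + 105 = 225 min to 120 + 120 = 240 min | 60 × 225/60 = 225 h to 60 × 240/60 = 240 h |

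**3. What this could mean in events**

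The documents give no rate; 10.1 says only that contrast allergy is rare. As an assumption, let a proportion p of sessions, from 0.1% to 2%, have a reaction that begins and resolves before the scan ends and is not recorded. Expected uncounted events are n × p, and the chance of at least one is 1 − (1 − p)^n.

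| Sessions n | p = 0.1% | p = 2% |
|---|---|---|
| 60 | 60 × 0.001 = 0.06; chance 5.8% | 60 × 0.02 = 1.2; chance 70.2% |
| 120 | 120 × 0.001 = 0.12; chance 11.3% | 120 × 0.02 = 2.4; chance 91.1% |

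**The case against.** The strongest reply is that only a strictly literal reading produces the gap and the surrounding text shows a different intent. Section 10.2 says all adverse events will be collected, 10.1 puts the examination itself under monitoring, and section 13 binds the trial to Good Clinical Practice. Sensible staff would probably record a reaction on the scanner. The intent is indeed clear, and this looks like a drafting fault. But a general phrase does not override an explicit definition, and relying on staff to disregard it is not a safeguard.

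The serious-event consequence is narrow. Admission or lasting disability would extend past the scan and be captured, as would any reaction that begins or persists afterwards. What remains is mainly a grave event that starts and ends before the scan is over. This limit stands.

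The event rates have no source in the documents, and the resulting range is too wide to guide a decision. This also stands. The point rests on the wording and the exposure time, not on those figures.

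The CRF, the adverse event reporting module and the two product dossiers are not among the documents and might set an earlier start. That lowers confidence that events would in practice be lost, but it does not correct the protocol's definition.

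Finally, 10.2 gives no end to the collection period, and changing the start alone would leave that open. This is fair, and the same amendment can deal with it.

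**Conclusion.** The definition is wrong as written. Followed literally, it leaves out signs and symptoms that begin and resolve during uptake or on the scanner. The gap is certain for the first session (105 to 120 minutes per patient) and depends on the reading for the second (225 to 240 minutes over both). The serious-event definition and the 24-hour rule inherit it.

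The times rest on the protocol's own approximate scan length and on its two uptake figures for 68Ga-Bombesin. They measure exposure, not lost events; how many events would be lost cannot be known from the documents. Safety is neither a primary nor a secondary aim, and no efficacy or accuracy result changes. The sponsor should correct this, but it does not threaten the main analysis.

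**What to change.** Reword 10.2 so that an adverse event is any untoward sign, symptom or condition, whether or not causally related, with onset from the first tracer administration onward, expressly including uptake and examination at both sessions. State that the serious-event definition and the 24-hour rule in 10.2 and 10.3 apply from the same start. Say in the same place when collection ends, which the protocol leaves open. If the CRF does not already do so, record the time of onset relative to tracer and contrast injection; this is useful for interpretation but secondary to the wording.

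The cost is a short amendment and, at most, one added CRF field. Slightly more events may be recorded. No dose, schedule or clinical management rule changes.

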10.3 Pharmacovigilance Procedure

Information about all serious adverse events will be collected and recorded on the Sample Adverse Event Reporting Module. To ensure Patient safety, all serious adverse events must be reported within 24 hours of the researcher who is aware of it.

11. TEMPORARY OR DEFINITIVE TREATMENT DISCONTINUATION

The patient can withdraw from the study at any time without giving reasons and he will not be in any way disadvantaged by this.

After 68Ga-PSMA and 68Ga-Bombesin PET/MR imaging, in case patients won't be available to be followed-up, 68Ga-PSMA PET/MR and 68Ga-Bombesin PET/MR imaging data will be evaluated and data will be equally used in order to assess the diagnostic accuracy of 68Ga-PSMA PET/MR and 68Ga-Bombesin PET/MR for the detection of the site/s of relapse (aim 1); to correlate 68Ga-PSMA PET/MR and 68Ga-bombesin-PSMA PET/MR imaging with clinical and pathological features (aim2) and to evaluate the results of a lesion-targeted approach in terms of biochemical-recurrence-free survival and clinical recurrence-free survival (aim 3).

12. STATISTICAL CONSIDERATIONS

12.1 Determination of sample size

The sample size was computed based on sensitivity analysis for predicting lymph node metastasis. Assuming an average prevalence of lymph node metastasis of 35%, a total sample size of 60 patients is sufficient for evaluating a sensitivity of 80% with an absolute precision of 18% (at 95% confident level).

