
STATISTICAL CONSIDERATIONS
	
The sample size was computed based on sensitivity analysis for PET/MR in predicting lymph node metastasis. Assuming an average prevalence of lymph node metastasis of 35%, a total sample size of 60 patients is sufficient for evaluating a sensitivity of 80% with an absolute precision of 18% (at 95% confident level).
 
8Ga-Bombesin PET/MRI and 68Ga-PSMA PET/MRI will be compared. Sixty patients treated with radical prostatectomy with biochemical recurrence of prostate cancer (PSA < 0.2 ng/ml and raising) will be evaluated and recruited in the study. They will be submitted to both 68Ga-PSMA PET/MR and 68Ga-bombesin PET/MR. Clinical and pathological variables will be recorded for each patient. The exact sites of recurrence as well as the size of all lesions will be recorded for all patients at both imaging procedures. A direct comparison between the two tracers will be performed using Chi-square test for categorical variables.
 
Univariable and multivariable logistic regression analyses will be used in order to identify the predictors of positive imaging at both 68Ga-PSMA PET/MR and 68Ga-bombesin PET/MR.
 
In patients with evidence of local recurrence submitted to salvage radiation therapy the biochemical response to radiotherapy will be used as confirmation of the positivity of imaging.
 
In patients with nodal only recurrence, a salvage pelvic and/or retroperitoneal lymph node dissection according to the site of the positive nodes will be proposed. For patients undergoing nodal dissection, a direct comparison between PET studies and histopathological examination in terms of site and size of the recurrent nodes will be performed. The performance characteristics of both 68Ga-PSMA PET/MR and 68Ga-bombesin PET/MR will be evaluated and compared through accuracy, sensitivity, specificity, positive and negative predictive value in a patient-based as well as in a lesion-based approach.
 
For the evaluation of the response to lesion-targeted treatments Kaplan-Meier analyses as well as univariable and multivariable Cox regression analyses will be performed.

DURATION OF STUDY PERIOD
	
Total duration of the study: 3 years.
 
Each patient will perform two PET/MRI studies in two different days. Each study will last

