5.2 Primary and secondary specific aims

Primary aim

To evaluate the diagnostic accuracy of 68Ga-PSMA PET/MR to identify the site of recurrence in patients with biochemical relapse of PCa after primary treatment and comparison with the performances of 68Ga-Bombesin PET/MR

Secondary aims

- To correlate 68Ga-PSMA PET/MR and 68Ga-bombesin-PSMA PET/MR imaging with clinical and pathological features.
- To evaluate the results of a lesion-targeted approach in terms of biochemical-recurrence-free survival and clinical recurrence-free survival. A particular effort will be made in order to identify patients that might benefit most from this approach in terms of predictors of both positive imaging findings as well as response to local treatment of metastatic sites with both surgery and radiation therapy.

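### The 60-patient justification holds for nodal sensitivity, but no precision or power is given for any-site accuracy or the paired tracer comparison, and no primary comparison is named

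*Combined protocol and SAP*

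**What the plan says.** Section 12.1 gives the only size justification: "The sample size was computed based on sensitivity analysis for predicting lymph node metastasis". It continues "Assuming an average prevalence of lymph node metastasis of 35" percent, and concludes that "a total sample size of 60 patients is sufficient for evaluating a sensitivity of 80% with an absolute precision of 18" percent at the 95% confidence level. The synopsis repeats the figures and words the basis as "The sample size was computed based on sensitivity analysis for PET/MR in predicting lymph node metastasis". Neither place names a tracer.

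The primary aim in section 5.2 (also in the synopsis) has two parts: "To evaluate the diagnostic accuracy of 68Ga-PSMA PET/MR to identify the site of recurrence", and "comparison with the performances of 68Ga-Bombesin PET/MR". Site of recurrence is wider than lymph nodes. Section 6.1 lists biopsy of suspected local recurrence and response to salvage radiotherapy among the reference standards. Section 6.1 also has every patient undergo both scans.

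For the analysis, the synopsis and section 12.2 name a Chi-square test for the tracer comparison. Both list accuracy, sensitivity, specificity and the two predictive values, at patient and lesion level. The synopsis says these will be evaluated and compared between tracers; section 12.2 says only that they will be evaluated. No measure or level is called primary.

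**The concern.** The plan's only statement that 60 patients are enough concerns one component of the primary aim (nodes) and one proportion at a time. For any-site accuracy and for the tracer comparison it states no precision, power, effect size or discordance rate. Nothing therefore tells a reader what size of tracer difference the study could resolve.

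Two consequences follow at reporting. A non-significant tracer test, given without an interval, can be taken as similar performance when the data may be compatible with a large difference. And with five measures at two levels and none primary, a single favourable contrast can be picked out afterwards. The choice of test adds to this, because an ordinary Chi-square test treats the two scans of one patient as independent samples.

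**Working it through.** **Inputs from the documents:** N = 60, nodal prevalence 35%, sensitivity 80%, precision 18 points, 95% confidence (12.1 and synopsis); both scans in every patient (6.1). **Assumed, because the documents do not give them:** the discordance rate (proportion of patients in whom the two scans disagree on the measure), the second tracer's sensitivity, and the number of evaluable patients.

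**1. The plan's own figure.**
- Node-positives needed: 1.96² × 0.8 × 0.2 / 0.18² = 18.97. Total: 18.97 / 0.35 = 54.2, so 55. Sixty is sufficient.
- Expected node-positives: 60 × 0.35 = 21. Half-width: 1.96 × √(0.16/21) = 17.1 points.
- Exact (Clopper-Pearson) interval at 17/21: 58.1% to 94.6%, an average half-width of 18.2 points.

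The stated 18 points is confirmed, for each scan's nodal sensitivity taken separately.

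**2. Any-site accuracy.** At an assumed 80%, the half-width is 1.96 × √(0.16/n): 10.1 points if all 60 are evaluable, 14.3 if 30 are.

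**3. Paired tracer difference.** Half-width = 1.96 × √((discordance − difference²)/n). With equal sensitivities (difference 0):

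| Assumed discordance | n = 21 | n = 60 |
|---|---|---|
| 10% | 13.5 | 8.0 |
| 16% | 17.1 | 10.1 |
| 20% | 19.1 | 11.3 |
| 30% | 23.4 | 13.9 |
| 40% | 27.1 | 16.0 |

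With both sensitivities at 80%, 40% is the largest discordance possible and 32% corresponds to independent scans. In 21 patients the difference is less precise than a single sensitivity (17.1) only above 16% discordance.

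**4. Power of the exact McNemar test, two-sided 5%, 80% versus 60%.** With these two values, discordance must lie between 20% and 60%.

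| Assumed discordance | n = 21 | n = 60 |
|---|---|---|
| 20% | 23% | 99% |
| 30% | 22% | 80% |
| 40% | 19% | 64% |
| 60% | 14% | 46% |

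**5. Ordinary Chi-square on paired data.** With both tracers at 80%, the test takes the variance of the difference as 2 × 0.8 × 0.2 / n = 0.32/n; the true variance is discordance/n. At 10% discordance its standard error is √(0.32/0.10) = 1.79 times too large, and at 20% it is √(0.32/0.20) = 1.26 times too large. Simulation with 21 or 60 patients gives a true error rate of about 0.1% at 10% discordance and 1.4-1.6% at 20%, instead of 5%. The more the scans agree, the more sensitivity to a real difference is lost.

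**The case against.** The scope of the calculation is disclosed: both places say that it concerns nodal metastasis, the arithmetic is right, and this is a phase II, open, uncontrolled study. All of that stands. No larger sample is called for.

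Four stronger readings are tempting, and the documents do not support them.

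- *The comparison, or the primary endpoint, must be far less precise than 18 points.* A reader might infer this from the small nodal subset. But pairing can make the comparison tighter (13.5 points at 10% discordance in 21 patients), and any-site accuracy could be estimated to about 10 points if all 60 are evaluable.
- *The study cannot detect a large tracer difference.* For a 20-point difference, power is low throughout the nodal subset. It is not shown to be low for any-site comparison, where 60 evaluable patients give 46-99%. How many will be evaluable is unknown, because verification follows routine care; 60 is a ceiling.
- *The plan runs ten significance tests.* Five measures at two levels are to be compared according to the synopsis only, and neither place says that each gets a test.
- *The exact interval exposes an error.* It reaches 23 points below 17/21 but averages 18.2 each way, which agrees with the stated figure.

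It can also be said that the plan claims neither equivalence nor non-inferiority, and that a paired form of the Chi-square test (McNemar) may have been meant. Both are fair. But the text names no paired test and no interval, so the matter is left open.

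**Conclusion.** The concern holds in limited form. The sample-size statement is correct for nodal sensitivity and silent on both parts of the primary aim as written. What the tracer comparison can deliver depends on two unstated quantities: the discordance rate and the number of evaluable patients. Over the assumed 10-40% discordance with equal sensitivities, its half-width runs from 8 points (60 patients) to 27.1 points (21 patients). Over the whole discordance range possible for 80% versus 60%, power runs from 14% to 99%.

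The part with practical weight is the analysis. No primary comparison is named, and the one stated test, read literally, ignores the pairing. At 10-20% discordance it would reject a true null in roughly 0.1-1.6% of trials rather than 5%. This is worth correcting before analysis, but it does not show that 60 patients are too few.

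**What to change.** No patients or scans need to be added.

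- **Section 12.2 and synopsis:** name one primary patient-level measure (correct site of recurrence) and one primary tracer comparison on that measure. Report it as a paired difference with a 95% interval and a paired test such as exact McNemar, in place of the plain Chi-square. Make the other measures, and the lesion-level results, descriptive. State that a non-significant result will not be read as equal performance. Align the two places on whether the measures are compared or only evaluated.
- **Section 12.1 and synopsis:** say that the 18 points applies to the nodal sensitivity of each scan only. Add the expected half-width of the paired difference over an assumed discordance range, for the node-positive subset and for the number of patients expected to be evaluable.

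The cost is rewording of three places. The downside is that the stated precision will look less favourable, and that most measures lose confirmatory standing.
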